## Background

Despite global efforts to control HIV among key populations, new infections among men who have sex with men (MSM) are still increasing. In the United States (US), HIV prevalence among MSM reached levels as high as 14.5% in 2015. In China, HIV prevalence among MSM increased from 0.9% in 2003 to 8.0% in 2015, and relatively unchanged since 2016. In addition, alarmingly high HIV incidence rates have been observed among MSM in several cities in China. HIV incidence is as high as 10.0/100 person-years among MSM in eight Chinese cities during 2016-2017. To address this challenge, HIV prevention strategies with high efficacy are urgently needed.

HIV Partner Services (PS), the process of informing potential risk of exposure to sexual partners, is a cornerstone of HIV prevention. PS are important for identifying cases, reducing re-infection rates, promoting linkage to care, and saving cost. HIV PS programs have been implemented in heterosexual populations in many settings and among MSM in many countries such as the US, Peru, and Australia. Studies conducted in the US demonstrated that PS is a cost-effective way to identify new cases, reduces the average duration of infection and reduces overall re-infection rates.

However, barriers from both health providers and index patients limit its efficacy. As a result, PS is underused in many countries, including China where only 15.7% of index HIV case spouses were notified. In addition, tailored PS for MSM who usually have multiple male or female partners are limited, especially in China. Conventional PS in China use passive referral by providing index patients with partner referral cards, and PS via disease intervention specialists is not available in China. One study conducted among Chinese MSM revealed that only 267/1225 (21.8%) partners of the index cases were successfully notified and tested. Our preliminary data showed that only 16.2% (18/111) of HIV infected MSM have notified their casual partners in 2016. The low frequency of routine PS programs suggests that current strategies reach only a fraction of those at risk. Many existing HIV PS programs lack a patient-centered focus and are ill-suited to addressing issues faced by many MSM. Few incorporate high-risk individual preferences are tailored to the needs and concerns of MSM, or incorporate preferences and suggestions from the local community. Thus, identifying an innovative method to improve the efficacy of PS is critical for HIV control in China and other middle-income countries. Successful PS programs for MSM in China and other LMICs will require novel methods to reach an MSM population where condomless sex and casual sexual partnerships are common, and where severe stigmatization restricts healthcare access among MSM.

We will apply community-based participatory research (CBPR) principles to our intervention development via crowdsourcing. By bringing together researchers and communities, CBPR recognizes the importance of involving members of a study population as active participants in all phases of the research process. CBPR or application of its principles to specific components of research may help reduce health disparities. Crowdsourcing is an approach that obtains solutions from communities. Crowdsourcing has been used effectively in public health to improve HIV testing, promote condom use, and monitor outbreaks. Informed by CBPR theory, we will use crowdsourcing tools so that MSM and other stakeholders can contribute their voices to design participant-oriented interventions. Based on our previous findings and a pilot PS crowdsourcing contest, crowdsourced messages developed for PS may resonate

more with MSM compared to traditional PS messages, leading to increased community participation and acceptance of HIV PS, and in turn, improving the efficacy of HIV PS.

We will use crowdsourcing (including open contest and designathon, a designathon is similar to a hackathon but focused on generating and creating designs) to develop promotional concepts, images, and videos for delivery on smartphones or computer. After the top finalists are chosen by a judging panel, the PS crowdsourcing materials will be delivered to each sexual partner through the index partners' preferred method (send by index partner, healthcare provider, an anonymous system, or any combinations). This approach will take advantage of the widespread availability of smartphones and the internet in China to increase the notification rate, while maintaining confidentiality. A social media-based PS program, taking advantage of smartphones and the internet, could be an important vehicle for anonymous and widely delivery of key messages to large portions of the target populations at low cost. For example, a study conducted in Peru indicated that web-based PS significantly increased the partner notification rate among MSM. The widespread use of smartphones makes this approach feasible, not only in China, but also in other countries throughout South Asia, Southeast Asia, and the US.

This study aims to describe the design of a pilot randomized controlled trial and to test the feasibility, acceptability, and preliminary impact of crowdsourced PS compared with conventional PS on promoting HIV testing uptake among partners of newly identified MSM cases in China. We hypothesize that a crowdsourced HIV PS approach, as compared to conventional PS using referral cards (standard of care in China), will yield more sexual partners reporting for HIV testing; and more sexual partners with confirmed HIV.

## Methods and study design

### Study design overview

This study will use a pilot RCT comparing the crowdsourced PS intervention to standard PS. In China, a passive referral is the only existing PS model for HIV PS. We will conduct a pilot study to refine the components and procedures of the intervention and test the feasibility and acceptability of the crowdsourced PS intervention. Newly identified MSM HIV cases will be recruited from Guangzhou. After completion of a baseline survey, eligible MSM will be randomized individually to either the crowdsourced intervention or conventional PS (control arm) in a 2:1 ratio. In both arms, partners will be instructed to report to the study site sites for HIV testing and will complete a brief sexual history questionnaire upon presentation. We will re-contact them within three months of enrolment to confirm whether the intervention or control PS procedures were implemented by the index. The primary outcome will be 1) the feasibility and acceptability of the intervention; 2) the preliminary impact of the intervention: by comparing the proportion of partners getting HIV testing between the intervention and control groups. Secondary outcomes will be the number of partners getting notified, the number of testing partners with confirmed HIV, and risk behaviors of partners. We will also observe these secondary outcomes among main male partners and casual partners separately. We hypothesize that: 1) a crowdsourced PS approach is feasible and acceptable, 2) as compared to conventional PS, will yield: a) more sexual partners reporting for HIV testing; b) more sexual partners getting notified; c) more sexual partners with confirmed HIV; and d) a set of sexual partners with greater STI risk behaviors, such as more receptive anal intercourse, and less condom use.

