## **Baseline questionnaire**

After enrolment, participants will complete a brief self-administered baseline questionnaire. Study staff will be available to assist in the event of confusion about specific questions or if participants do not have a sufficient reading level to complete the survey on a tablet. The questionnaire will address socio-demographic characteristics and HIV testing history. A more detailed, partner-centric sexual history will be obtained by focusing on sexual partners in the previous six months. The sexual history will include specific behaviors with individual partners, including receptive/insertive anal sex, performing/receiving oral sex, condom use, and frequency of each type of intercourse. Information on sexual orientation and sexual orientation disclosure status will also be collected. Detailed contact information will be obtained for the participants and sexual partners for the past six months. Contact information will include phone number, email address, WeChat ID, QQ ID, and smartphone-based sex-seeking applications ID (i.e., Blued ID).

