## **Index follow-up survey**

Three months after enrolment, index participants in both arms will be re-contacted by phone or email and provided a link to an online survey. A small incentive (mobile top-up) will be provided. The survey will further evaluate the acceptability and feasibility of the crowdsourced intervention among participants in the intervention group. We will also evaluate the potential challenges and advantages of the crowdsourced intervention. The survey will be comparable to the baseline survey. Sexual contact with specific partners, named previously, will be elicited, as well as new partners. The survey will also address whether the specific partners were notified by the index, underwent HIV testing, and how testing was performed.

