## **Study measures and outcomes**

### **Primary outcomes**

The primary outcomes are: 1), the feasibility of the study and the feasibility of the intervention. The feasibility of the study will be measured in the ability to enroll 120 newly identified MSM HIV cases as index participants in the study center in a 12-month period, and the ability to

contact the index MSM (follow-up rate) and their partners at 3 months after enrolment (proportion of the surveyed partners response to the survey). The feasibility of the intervention will be used to measure whether the crowdsourced intervention is successfully used or carried out. This will be measured in the frequency of the partners in the intervention arm receiving the crowdsourced intervention and the frequency of the partners taking action after they receive the intervention (whether go for HIV testing). 2), the acceptability of the crowdsourced intervention: this will be measured at baseline among index participants and the partners of the index participants in the intervention arm. We will ask the index participants and their partners whether the crowdsourced intervention is acceptable to them. 3), the preliminary impact of the intervention: the proportion of partners returning for HIV testing within 3 months of the index participant's enrolment in the study, determined based on the partners presenting to the centers and those verified from the CDC electronic medical record central database.

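### The plan allows study re-contact inside the 3-month window in which partner tests are counted, and its sections disagree on when contact happens and whether partners are included

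*Combined protocol and SAP*

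**What the plan says.** Three sections of the combined protocol and SAP describe follow-up contact.

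- **Study design overview.** "We will re-contact them within three months of enrolment to confirm whether the intervention or control PS procedures were implemented by the index". The referent of *them* is not stated. The sentence just before it covers the two arms together: "partners will be instructed to report to the study site sites for HIV testing and will complete a brief sexual history questionnaire upon presentation".
- **Index follow-up survey.** "Three months after enrolment, index participants in both arms will be re-contacted by phone or email". Only index participants are named. The survey asks "whether the specific partners were notified by the index, underwent HIV testing, and how testing was performed".
- **Primary outcomes.** Study feasibility includes the ability to "contact the index MSM (follow-up rate) and their partners at 3 months after enrolment". A parenthesis expresses the partner part as the response proportion among surveyed partners. That group is not defined, and is not limited to one arm or to partners who presented.

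Two further passages bear on the point. The impact outcome is "the proportion of partners returning for HIV testing within 3 months of the index" participant's enrolment, and the Statistical Analysis Plan repeats that window. The Baseline questionnaire section says: "Detailed contact information will be obtained for the participants and sexual partners for the past six months". Under the overview, the baseline survey precedes randomization, so these details are held for both arms.

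No section says that outcome counting closes before follow-up contact begins, or how a test that follows study contact is treated.

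**The concern.** The measurement can act on what it measures. An index man asked, partner by partner, who has been notified and tested is reminded of those he has not told. A partner who has not been tested, if the study contacts him, may be prompted to test. If either contact comes before the three months are up, a resulting test counts in the primary impact outcome although neither assigned procedure produced it.

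At the time of contact, the arm with the lower return rate has more untested partners left to prompt. Equal prompting in both arms therefore lifts that arm more and narrows the difference. If the intervention works as hypothesised, that arm is the control. What is at stake is mainly planning. The protocol says the pilot is not powered to compare the arms, but that its data will be used to size the full trial. A control rate raised by study contact would no longer describe card-based passive referral alone.

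**Working it through.** **1. Timing, side by side**

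| Section | When | Who |
|---|---|---|
| Study design overview | within three months of enrolment | *them*, unspecified |
| Index follow-up survey | three months after enrolment | index participants, both arms |
| Primary outcomes (feasibility) | at 3 months after enrolment | index men and their partners |
| Primary outcomes (impact), SAP | tests within 3 months of index enrolment are counted | partners |

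The first row lies inside the window of the fourth. The second and third rows fall at its close. No section gives a window in days.

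**2. The plan's own figure**

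Inputs from Sample size and power: 40 control, 80 intervention, control return rate p1 = 0.30, alpha 0.05 (taken as two-sided), power 0.80, minimal detectable effect 26.7 points, so p2 = 0.567.

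- Pooled rate: (40 × 0.30 + 80 × 0.567)/120 = 0.478.
- Standard error under no difference: √[0.478 × 0.522 × (1/40 + 1/80)] = 0.0967.
- Standard error under the alternative: √[0.30 × 0.70/40 + 0.567 × 0.433/80] = 0.0912.
- Power: Φ[(0.267 − 1.96 × 0.0967)/0.0912] = Φ(0.85) = 80.2%.

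Solving the same formula for exactly 80% power gives 26.6 points, so the stated figure reproduces.

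**3. Illustration of prompting**

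Let c be the share of otherwise untested partners whom study contact prompts to test before the window closes. The documents do not give c. The range 0 to 20% is an assumption. With the same c in both arms:

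- new rate = p + c(1 − p)
- new difference = (1 − c)(p2 − p1)

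| c | Control | Intervention | Difference | Power, same formula |
|---|---|---|---|---|
| 0 | 30.0% | 56.7% | 26.7 points | 80% |
| 5% | 33.5% | 58.9% | 25.4 points | 75% |
| 10% | 37.0% | 61.0% | 24.0 points | 71% |
| 20% | 44.0% | 65.4% | 21.4 points | 61% |

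For c = 10%: control 0.30 + 0.10 × 0.70 = 0.370; intervention 0.567 + 0.10 × 0.433 = 0.610; difference 0.90 × 0.267 = 0.240.

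c combines the share of untested partners reached early (directly or through the index) with the share of those who then test. If half are reached and 10% of those respond, c = 0.5 × 0.10 = 5%. If all contact comes after the window closes, c = 0.

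Like the protocol, these figures treat 80 and 40 as independent units and ignore clustering of partners within index. The 56.7% is the control rate plus the detectable effect, not a forecast.

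**The case against.** A reader might infer that the plan sets out to notify control-arm partners during the window, so that follow-up delivers part of the intervention to the control arm. The documents do not support that reading.

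- *Them* in the overview may mean the index men, as in the dedicated follow-up section. It may also mean the partners in the preceding sentence, who are described as presenting for testing and whom re-contact could hardly prompt.
- The only partner questionnaire described is the one completed on presentation. No section sets out a call or script for partners known only from the index's list. Holding their contact details shows that contact is possible, not that it is intended, and the details also serve message delivery and linkage.
- The two more specific sections put contact at three months, as the window closes. On that reading little or no prompted testing would count.
- Follow-up is planned in both arms, so an effect confined to control partners (7 points at c = 10%, from 0.10 × 0.70) has no basis in the text.
- Partner-by-partner questions are how index-reported notification, a secondary outcome, is obtained. Some reactivity to them is ordinary.

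All of this stands, and it limits the point. It does not remove it. The overview still permits contact before the window closes, Primary outcomes still extends contact to an undefined group of partners, and nothing says how tests after contact are counted. Staff following the overview in good faith could survey early.

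**Conclusion.** The conflict in timing and in who is contacted is real and should be resolved before follow-up starts. The bias is possible, not planned. It arises only if contact precedes the close of the window and reaches, directly or through the index man, partners who are still untested. If the intervention raises testing and prompting is similar in both arms, the result would be a smaller difference and a higher control rate. The 26.7 to 24.0 points at c = 10% is an illustration, because c cannot be estimated from the documents. The consequence is for the estimates handed to the full trial rather than for a test the pilot is not powered to make.

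A reader might also infer that 3-month partner contact must be limited to those who have presented. That does not follow. It would redefine a primary feasibility measure by a post-randomization event that may differ by arm, which is a trade-off for the sponsor to weigh.

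**What to change.** 1. Reconcile Study design overview, Index follow-up survey and Primary outcomes on who is re-contacted and when, and replace *them* with the intended group.
2. Define the three-month window in days from index enrolment, for example day 90. In both arms, send the index follow-up survey and any partner follow-up contact only after it closes.
3. In Primary outcomes and the SAP, count partner tests for the impact outcome by date of test within the window, whenever they are ascertained. The outcome is determined from presentation at the centers and the CDC database, so a later survey does not remove its source.
4. Define which partners are the surveyed partners in the feasibility measure, including whether they must have presented.

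The cost is protocol wording and a short shift in survey date. The downside is slightly longer recall for index participants. No added sample size or data collection is needed.

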## **Study site**

The study will take place in Guangzhou MSM community service center. The center is supported by the Guangzhou CDC to provide HIV testing for MSM. Guangzhou MSM community center provides services for 8000 MSM each year, and all the newly identified MSM HIV positive cases in Guangzhou will be referred to the center for additional service. Given 12 months of enrolment, we have a strong ability to recruit 120 eligible MSM (Guangzhou city newly identified 950 MSM HIV cases in 2017).

## **Eligibility**

Eligibility criteria include: (1) being born as a male, (2) 18 years old or elder, (3) at least one male or transsexual oral or anal sexual partner in the past six months, (4) newly identified as HIV positive, and (5) currently live in Guangzhou and no plan to leave Guangzhou in the following two months. To establish linkages for follow-up surveys, unique ID and access codes will be issued to each participant. Participants' phone number, email address, WeChat ID and Blued ID will be collected as tracking information for follow-up. Use of WeChat to contact participants will be particularly helpful given its broad uptake—846 million monthly active users as of November of 2016 and our previous experience in using WeChat to follow up over 80% of participants (1381 MSM). Unlike with phone numbers, people usually maintain a single WeChat account, even if they switch to a new phone number. Signed informed consent will be required from all participants.

## **Baseline questionnaire**

After enrolment, participants will complete a brief self-administered baseline questionnaire. Study staff will be available to assist in the event of confusion about specific questions or if participants do not have a sufficient reading level to complete the survey on a tablet. The questionnaire will address socio-demographic characteristics and HIV testing history. A more detailed, partner-centric sexual history will be obtained by focusing on sexual partners in the previous six months. The sexual history will include specific behaviors with individual partners, including receptive/insertive anal sex, performing/receiving oral sex, condom use, and frequency of each type of intercourse. Information on sexual orientation and sexual orientation disclosure status will also be collected. Detailed contact information will be obtained for the participants and sexual partners for the past six months. Contact information will include phone number, email address, WeChat ID, QQ ID, and smartphone-based sex-seeking applications ID (i.e., Blued ID).

## **Randomization**

Eligible participants will be randomly assigned to the crowdsourced PS arm (intervention arm) or conventional PS (control arm) in a 2:1 ratio. Since information under the control situation is already available from Guangzhou, a 2:1 ratio will allow us to spend more resources on intervention, and collect more primary outcome relevant data from participants in the intervention group (especially for the measure of the feasibility and acceptability). This approach ensures that the index participants in each arm will be evenly distributed. The number of partners

may vary somewhat across the two arms, as the number of partners of the index participants is variable. However, the total number of partners in the two arms should be comparable.

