### Sample size and power

This is a pilot RCT, and the primary outcomes of this study are: 1) to test the feasibility and acceptability of the crowdsourced intervention, and 2) to pilot the preliminary impact of crowdsourced PS intervention in promoting HIV testing among partners of the newly identified HIV cases. In addition, this pilot RCT aimed to collect preliminary data for the designing of a full RCT, which aimed to measure the efficacy of the crowdsourced PS intervention in promoting PS. Thus, the sample size of this study is not designed and will be not powered enough to test the difference between the two arms. However, with a sample size of 120 (80 for intervention arm and 40 for the control arm, respectively), this pilot study would collect enough information to measure the feasibility and acceptability of the intervention, and it will be able to observe the differences between the two arms and collect preliminary data for an adequate sample size calculation of a full RCT. With a sample size of 120 (ratio of 2:1), alpha=0.05, power=0.80, and the partner return rate in the conventional PS arm is 30% (around 31% in 2016 in Guangzhou), the minimal detectable effect size would be 26.7% for this pilot study.

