## Statistical Analysis Plan

For the primary outcomes of feasibility and acceptability of the intervention: this will be analyzed through descriptive analysis to assess the feedback on the feasibility and acceptability of the crowdsourced PS intervention among index MSM and their partners in the intervention group. For the primary outcome of the proportion of partners returning for HIV testing within 3 months of the index participant's enrolment in the study, log-binomial regression (generalized linear model with binomial distribution and log link) will be used to calculate 95% confidence intervals for the proportion of notifiable partners visiting by arm. Risk differences and risk ratios will also be calculated in these models. As this study is a pilot RCT, and we will only recruit 120 index MSM, and they will be randomly assigned in a 2:1 ratio, adjustment for covariates would be necessary if the two study arms are not balanced. In secondary analyses, we will adjust for pre-specified potential confounding variables that might bias the estimate if not accounted for (e.g. index age, index marital status). If a partner reports more than one index referred him, he will be counted as a returning partner for each identified index.

*Table 1* Analysis strategies for secondary outcomes

Secondary Outcome	Population	Model Type
The proportion of reported partners being notified by indexes among all reported partners	Reported sexual partners	Binomial regression, robust variance
Mean number of partners tested per index participant	Index participants	Poisson or negative binomial regression, robust variance
The proportion of positive HIV tests among tested partners	Tested sexual partners	Binomial regression, robust variance
Mean number of partners with HIV (case-finding) per index participant	Index participants	Poisson or negative binomial regression, robust variance
The proportion of reported partners getting HIV testing who are not spouses or regular partners	Reported casual male sexual partners	Binomial regression, robust variance
The proportion of presenting partners reporting condom use during the last anal intercourse	Presenting sexual partners	Binomial regression, robust variance

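### Random 2:1 assignment does not ensure evenly distributed index participants, and the per-index count models omit the baseline partner count that would absorb the resulting chance imbalance

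*Combined protocol and SAP*

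**What the plan says.** The Study design overview states that, after the baseline survey, "eligible MSM will be randomized individually to either the crowdsourced intervention or conventional PS (control arm) in a 2:1 ratio". The Randomization section repeats the ratio and concludes: "This approach ensures that the index participants in each arm will be evenly distributed". It then concedes that partner numbers may differ somewhat between arms. No section describes how the sequence is generated, or any blocking, stratification or minimization.

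Sample size and power relies on a fixed split, "80 for intervention arm and 40 for the control arm, respectively", for its detectable difference of 26.7%.

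The Statistical Analysis Plan allows for imbalance: "adjustment for covariates would be necessary if the two study arms are not balanced". It offers index age and marital status as examples of adjustment variables. Table 1 assigns Poisson or negative binomial regression with robust variance to partners tested per index and to partners with HIV per index. It names no covariate or offset for either.

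The Baseline questionnaire section collects a partner-by-partner sexual history for the previous six months, so the number of listed partners is available before allocation.

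**The concern.** Random assignment balances the arms on average over repeated trials. In one trial with about 40 controls it guarantees nothing, so the sentence claims a property that the described method does not have. The SAP's own provision for unbalanced arms concedes this.

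Partner load is where it matters. A man with more partners can bring in more tested partners whichever arm he is in. A few high-partner men falling by chance in the smaller arm can move a per-index mean with no intervention effect. The pilot is meant to supply figures for sizing a full trial, and to show which secondary outcomes discriminate well enough to carry forward. Avoidable noise in the per-index outcomes makes both uses less reliable.

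**Working it through.** **1. The plan's own figure.** Inputs from Sample size and power: 80 and 40, "alpha=0.05, power=0.80", control rate 30%. I assume a two-sided test with pooled variance.
- Pooled rate at 30% against 56.7%: (40×0.30 + 80×0.567)/120 = 0.478.
- Null SE: √[0.478×0.522×(1/40+1/80)] = 0.0967.
- Alternative SE: √[0.30×0.70/40 + 0.567×0.433/80] = 0.0912.
- z = (0.267 − 1.96×0.0967)/0.0912 = 0.85, so power is 0.80. The 26.7% reproduces; the exact solution is 26.6 points.

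**2. Drift in the split, if assignment were simple.** Control arm size follows Binomial(120, 1/3), with SD √(120×1/3×2/3) = 5.2 and 95% range 30 to 50. Exactly 40 occurs 7.7% of the time.
- 90/30: variance ratio (1/30+1/90)/(1/40+1/80) = 1.185, SE up 8.9%, detectable difference 28.9 points.
- 70/50: variance ratio 0.914, SE down 4.4%, detectable difference 25.4 points.
- Averaged over all splits: variance up 1.3%.

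**3. Drift in partner load.** The 95% chance difference in mean partners per man, relative to the mean, is 1.96×CV×√(1/40+1/80) = 0.38×CV. The CV is not in the documents. At assumed CVs of 0.5, 1.0 and 1.5 this gives ±19%, ±38% and ±57%.

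**4. Effect on partners tested per index.** Let each man list m partners (mean μ, SD σ), each tested with probability p, with within-man correlation ICC. For 80/40 and no intervention effect:

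Var(log ratio) ≈ (A + B)×(1/40+1/80), where
- A = (σ/μ)², the part due to partner load;
- B = [(1−p)/p]×[μ + ICC×(μ²+σ²−μ)]/μ², the rest.

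Full adjustment for partner count removes A. With p = 0.30 (the plan's control rate) and ICC = 0.1 (assumed):

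| Assumed mean, SD | A | B | SD unadjusted | SD without A | Reduction |
|---|---|---|---|---|---|
| 2.5, 1.8 | 0.518 | 1.194 | 0.253 | 0.212 | 16% |
| 3.6, 2.5 | 0.482 | 0.929 | 0.230 | 0.187 | 19% |
| 3.6, 3.7 | 1.056 | 1.063 | 0.282 | 0.200 | 29% |
| 5, 6 | 1.440 | 0.989 | 0.302 | 0.193 | 36% |

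Simulated trials with simple 2:1 assignment agree. Unadjusted SDs were 0.262, 0.235, 0.284 and 0.300. A Poisson model with log partner count, fitted to a further 2,000 simulated trials per row, gave 0.222, 0.193, 0.210 and 0.198.

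**5. Allocation or model?** In one simulation of this kind, the SD of the log ratio was:
- simple assignment, unadjusted: 0.281;
- simple assignment, strata 1, 2–3, 4+ in the model: 0.240;
- simple assignment, log partner count in the model: 0.198;
- allocation stratified on those strata, unadjusted: 0.236.

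Most of the gain comes from the covariate.

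**6. Partners with HIV per index.** This count is sparser, so B dominates. In the 3.6, 3.7 row:
- If 20% of tested partners are positive (assumed), p = 0.3×0.2 = 0.06 and B = 7.14. The SD falls from 0.554 to 0.517, or 7%.
- At the 8.0% prevalence quoted in Background, p = 0.024 and B = 18.5. The SD falls from 0.857 to 0.834, or 3%.

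**7. Primary risk difference.** With mean 3.6, SD 3.7, control testing of 50% for main and 22% for casual partners, and ICC 0.1 (all assumed), stratified allocation moves its SD only from 5.5 to 5.4 points.

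**The case against.** The case on the other side is substantial.

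- **Silence is not a plan.** The documents do not say that allocation is unrestricted, and the disputed sentence may be a loose description of a blocked scheme. This stands: the supportable statement is that no method is described. A reader might infer that no blocking or stratification is planned; the text does not show that. The ranges in steps 2 and 5 are conditional on simple assignment.
- **The split hardly matters.** This stands. A reader might infer that the 26.7% is undermined by drift from 80/40, but drift towards equal arms improves precision and the average cost is about 1%.
- **Chance imbalance is not bias.** This stands. Robust-variance intervals would reflect it. What is lost is precision.
- **The SAP already allows adjustment, with an open list of variables.** This stands only in part. Adjustment depends on imbalance being seen, with no criterion given. Partner count is not named, and Table 1 carries no covariate. The precision gain is there whether or not the arms look unbalanced.
- **These are secondary outcomes in a pilot stated not to be powered for comparing arms.** True, and it limits the weight of the point. The pilot's use in planning the full trial keeps it worth making.
- **The inputs are assumed.** True. The documents give no partner mean or SD, so only a range can be offered.

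**Conclusion.** The point holds in a limited form. The assurance of even distribution is not supported by the method described and should be replaced. The practical cost lies in the per-index count models. For partners tested, leaving out baseline partner count gives an SD of the log ratio of about 0.23 to 0.30, against about 0.19 to 0.22 with log count in the model. That is a reduction of roughly 16% to 36% by formula across the four assumed distributions. For partners with HIV the reduction is only about 3% to 7% in the scenario worked. These sizes rest on the assumed partner distributions, 30% testing, an ICC of 0.1 and no intervention effect.

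A reader might conclude that the trial needs stratified randomization. The calculations do not support that: simple assignment with log partner count in the model does better than stratified allocation left unadjusted. Stratifying is a reasonable option, not a requirement.

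**What to change.** **Statistical Analysis Plan and Table 1.** Add for both per-index count outcomes: *The model will include the number of partners listed in the baseline sexual history (log count) as a covariate, whether or not the arms differ on it.* Strata of 1, 2–3 and 4 or more are an acceptable substitute but recover less. Eligibility requires at least one partner, so the log should be defined. With a log link and a constant ratio between arms, the adjusted ratio targets the same quantity as the unadjusted one.

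**Randomization section.** Delete the assurance and state the sequence method actually used, for example computer-generated 2:1 permuted blocks of varying size, optionally stratified by listed partner count.

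**Cost.** One extra model term, using data already collected, and a few lines of text. If allocation is stratified, incomplete blocks may leave the split slightly off 80/40, and short blocks at a single site where staff know the arm make some assignments partly predictable.
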